18.2 EARLY TERMINATION OR SUSPENSION OF AN INVESTIGATION

Sight Sciences may terminate the study, in which case the investigators and associated IRBs will be notified in writing. Possible reasons for study termination include but are not limited to:

- The discovery of an unexpected, significant, or unacceptable risk to the study subjects treated with the device
- Insufficient enrollment in the study
- Withdrawal of FDA listing of the TearCare product.

Sight Sciences reserves the right to stop the study at a center any time after the initiation visit if there have been no subject enrollments or if significant protocol/deviations are observed at the site.

Likewise, a principal investigator may terminate the study at his/her institution. This decision must be followed by written notification to Sight Sciences within five working days, stating the reasons for termination.

If the study is terminated, every effort should be made to obtain final follow-up from all subjects.

In the event that there are significant human use issues with the device, the investigator will be consulted to make a determination of whether the study should be terminated or not.

18.3 INVESTIGATOR RESPONSIBILITIES

18.3.1 GENERAL RESPONSIBILITIES OF INVESTIGATORS

An Investigator is responsible for ensuring that an investigation is conducted according to the signed agreement, the investigational plan and applicable FDA regulations, for protecting the rights, safety, and welfare of subjects under the Investigator's care, and for the control of devices under investigation. An Investigator also is responsible for ensuring that informed consent is obtained in accordance with 21 CFR part 50.

18.3.2 SPECIFIC RESPONSIBILITIES OF INVESTIGATORS

1. Awaiting approval - An Investigator may determine whether potential subjects would be interested in participating in an investigation, but shall not request the written informed consent of any subject to participate, and shall not allow any subject to participate before obtaining IRB approval.
2. Subject Qualification - The Investigator is responsible for ensuring that all subjects entering the study conform to the patient selection criteria.
3. Compliance - An Investigator shall conduct an investigation in accordance with the signed agreement with the Sponsor, the investigational plan, all applicable FDA regulations, and any conditions of approval imposed by an IRB.

18.3.3 INVESTIGATOR RECORDS

A participating Investigator shall maintain the following accurate, complete, and current records relating to the Investigator's participation in an investigation for the period specified in Section 14.6:

1. All correspondence with another Investigator, an IRB, the Sponsor, a monitor, or FDA, including required reports.
2. Records of each subject's case history and exposure to the device. Case histories include the study CRF's/worksheets and supporting data including, for example, signed and dated consent forms and medical records. Such records shall include:
 - a) Documents evidencing informed consent.

- b) All relevant observations, including records concerning adverse device effects (whether anticipated or unanticipated), information and data on the condition of each subject upon entering, and during the course of, the investigation, including information about relevant previous medical history and the results of all diagnostic tests.
- 3. The protocol, with documents showing the dates and reasons for each deviation from the protocol.
- 4. Any other records that FDA requires to be maintained by regulation or by specific requirement for a category of investigations or a particular investigation.

18.3.4 INVESTIGATOR REPORTS

An Investigator shall prepare and submit the following complete, accurate, and timely reports:

- 1. Unanticipated Adverse Device Effects - An Investigator shall submit to the Sponsor and to the reviewing IRB a report of any unanticipated adverse device effect occurring during an investigation as soon as possible, but in no event later than 10 working days after the Investigator first learns of the effect.
- 2. Withdrawal of IRB Approval - An Investigator shall report to the Sponsor, within 5 working days, a withdrawal of approval by the reviewing IRB of the Investigator's part of an investigation.
- 3. Progress - An Investigator shall submit progress reports on the investigation to the Sponsor, the monitor, and the reviewing IRB at regular intervals, but in no event less often than yearly.
- 4. Deviations from the Investigational Plan - An Investigator shall document and report to the Sponsor any deviation from the investigational plan.
- 5. Informed Consent - If an Investigator enrolls a subject without obtaining informed consent, the Investigator shall report such use to the Sponsor and the reviewing IRB within 5 working days after the use occurs.
- 6. Final Report - An Investigator shall, within 3 months after termination or completion of the investigation or the Investigator's part of the investigation, submit a final report to the Sponsor and the reviewing IRB.
- 7. Other - An Investigator shall, upon request by a reviewing IRB or FDA, provide accurate, complete, and current information about any aspect of the investigation.

18.4 INVESTIGATOR AGREEMENT

The principal investigators in each center shall agree to the clinical protocol and any amendments and indicate their approval and agreement by signing and dating the cover page of the study protocol and the Investigator Responsibility Agreement.

19 PUBLICATION POLICY

Sight Sciences recognizes the value of disseminating research results. It is understood that the Study is part of the Multi-Center Clinical Trial and publication of results is expected. This publications policy applies to journal articles, conference abstracts, and conference presentations (posters and slides) covering Sight Sciences-sponsored clinical studies. This policy is in addition to any arrangement contained in the Clinical Trial Agreement between Sight Sciences and the investigator.

Multi-Site Data

Clinical site investigators are encouraged to propose publications and abstracts that include clinical or research data from multiple clinical sites; such projects will be coordinated by Sight Sciences. Authorship of papers and abstracts resulting from these projects will be determined collaboratively according to the following guidelines:

- The first author on such publications will be the person who primarily wrote the paper and took the lead on the research. In the case of clinical trial papers where all authors contributed equally, authorship order may be based on site enrollment or other criteria at Sight Sciences' discretion.
- Other authors include those who significantly contributed to the specific work.
- At least one person from each clinical site whose study subjects appear in the work will be acknowledged in the manuscript/presentation in some way, either as an author group member, a non-author contributor, or listed in the acknowledgements, depending on the particular policies of the journal or conference.

Single Site Data

After publication of the multi-center study results in a peer-reviewed journal, or if Sponsor has not submitted a manuscript for publication in a peer-reviewed journal within twelve (12) months after the study has been completed, whichever occurs first, Investigators may publish the results of the Study generated by the Investigator, subject to the obligations of the Clinical Trial Agreement between Sight Sciences and the Investigator, and the prior approval of Sponsor in writing.

Publications Review Policy

Investigators must submit all presentations, posters, abstracts and manuscripts pertaining to this study to Sight Sciences for review in advance of their submission. Sight Sciences conducts this review to protect its proprietary rights to information, inventions, or products developed under the Study. Please use the following guideline to determine the absolute minimum advance time for submitting an item to Sight Sciences for review:

- Presentations/Posters: 5 business days in advance of presentation
- Abstracts: 5 business days in advance of submission
- Manuscripts: 30 calendar days in advance of submission for publication

In accordance with the Clinical Trial Agreement, these items must receive written approval from Sight Sciences in order for them to be submitted or presented. If an item is not received in the timeframe listed above, approval may not be granted due to insufficient time for considered review. In addition, since most of our Clinical Trial Agreements require that Sight Sciences has 60 days to review publications, Sight Sciences reserves the rights granted in those Agreements if circumstances require a longer review.

21 APPENDIX A – METHODS FOR EXAMS, TESTS AND QUESTIONNAIRES

21.1 MEDICATIONS

When recording medications that the subject is taking, be sure to ask the subject to list any over-the-counter medications and supplements they are taking that could affect dry eye disease including, for example, cold medicines, Benadryl, fish oil supplements and Omega 3 products, retinol products, Latisse, etc. Multivitamins and general health supplements do not need to be recorded.

21.2 MANIFEST REFRACTION AND VISUAL ACUITY

Masked assessment: This assessment should be performed by the masked assessor.

Best-corrected visual acuity will be measured using the ETDRS method. Subjects should undergo manifest refraction prior to the ETDRS test, with the exception of the Day 1 and week 2 follow-up visit. On Day 1 and week 2, the subject's best spectacle corrected visual acuity (BSCVA) (i.e., without manifest refraction) will be measured using the ETDRS method. If the subject's visual acuity has worsened by ≥ 10 letters from baseline, then manifest refraction should be performed and the ETDRS measurement should be repeated.

Manifest Refraction

Refraction will be performed by the Investigator or staff using standard clinical practice.

ETDRS Testing Methods

Test Set-up

Best-corrected visual acuity at Baseline and all scheduled follow-up visits will be measured using the ETDRS charts at 1 or 4 meters.

The ETDRS chart must be placed at a distance of 4.00 meters (13 feet and 1.5 inches, or 157.5 inches) from cornea to chart surface, when using a 4-meter chart. For testing at 1 meter, the distance must be 1.00 (39 and 3/8 inches). A measuring tape or meter stick should always be available to verify the chart distance, even if the examining chair is supposed to be immovable or if reference marks are placed on the floor or walls.

The 1-meter distance is measured from the eye of the participant, seated comfortably in a chair with his/her back firmly placed against the chair, to the center of the 2nd or 4th letter of the 3rd line of the chart.

Note: If it is necessary to refract at the 1-meter distance, remember to add +0.75 sphere to the trial frame. Subtract the +0.75 sphere from the final refraction obtained at the 1-meter distance before recording the refraction on the form.

Methods

Starting at 4 meters, the subject should attempt to read each letter, line-by-line, left to right, beginning with line 1 at the top of the chart. If the subject is unable to read line 1 (20/200) at 4 meters, then visual acuity testing should be performed at 1 meter.

The subjects should be told that the chart has letters only, no numbers. If the subject reads a number, he or she should be reminded that the chart contains no numbers, and the examiner should then request a letter in lieu of the number. The subject should be asked to read slowly, about one letter per second, so as to achieve the best identification of each letter. He/she is not to proceed to the next letter until he/she has given a definite response.

A maximum effort should be made to identify each letter on the chart. When the subject says he/she cannot read a letter, the subject should be encouraged to guess. If the subject identified two (2) letters (e.g., A or B), the subject should be asked to choose one letter and, if necessary, to guess. When it becomes evident that no further meaningful readings can be made despite encouragement to read or guess, the examiner should stop the testing for that eye. However, all letters on the last line should be attempted as letter difficulties vary and the last letter may be the only one read correctly. The number of letters missed or read incorrectly should be noted.

In order to provide standardized and well-controlled assessment of visual acuity, all visual acuity assessments for a subject should be performed consistently (e.g., the same lighting conditions, viewing distance, etc.) at each visit.

Recording and Scoring Best-Corrected Visual Acuity

Using the Visual Acuity Worksheet, circle each letter the subject identifies correctly, write total correct for each row in the place provided, and compute the total correct for all rows. Do not mark letters read incorrectly or not read at all. Each letter read correctly is recorded as one. Only move to the next line if 4 or more letters are read correctly. If 3 or more letters are read correctly in the final line, then that line is used for the Snellen equivalent and the visual acuity score. If 2 or fewer letters are read correctly

in the final line, letters read from that line are added to the total visual acuity score and the previous line is used for the Snellen equivalent.

The number of correct letters will be recorded on the study worksheets and entered into the EDC. For the Day 1 Visual Acuity measurement, if two measurements are made, one BSCVA and one with manifest refraction, the latter VA obtained with manifest refraction should be entered into the EDC.

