9 STUDY PROCEDURES

9.1 STUDY SCHEDULE

Table 3: Study Visit Schedule

Visit (Visit Window)	Baseline (Day -7 to 0)	Treatment ^b (Day 0)	Day 1 (Day 1)	Week 2 (Day 12-16)	1 Mo (Day 21 – 35)
Informed Consent	X ^a				
Demographics, Ocular & Medical History	X				
Medication use	X			X	X
Questionnaires: OSDI, SANDE, Eye Dryness Score	X				X
Manifest Refraction and Best-corrected visual acuity (ETDRS)	X		X ^c	X ^c	X
Slit Lamp Exam	X		X	X	X
Tear Breakup Time	X			X	X
Corneal Staining	X			X	X
Conjunctival Staining	X			X	X
Schirmer 1 Test (without anesthesia)	X				
Meibomian Gland Secretion Scoring	X			X	X
IOP^d	X		X	X	X
Subject Eligibility	X				
Randomization	X				
TearCare or LipiFlow Treatment		X			
AE Assessment	X	X	X	X	X
Discomfort/Pain Questionnaire		X	X		
Collect Eye Drop/Lubricant Log					X

^a Subjects may sign the informed consent up to 30 days in advance of the baseline visit.

^b The TearCare or LipiFlow treatment must be performed within 7 calendar days of the Baseline visit. If scheduling permits, it may be performed on the same day as the Baseline visit following Randomization. Refer to Section 9.5.1 for details.

^c On Day 1 and Week 2, Best Corrected Spectacle Visual Acuity (BCSVA using EDTRS) is measured without manifest refraction (MR). If the VA has worsened by ≥ 10 letters (per ETDRS) from baseline, then MR should be performed, the ETDRS measurement should be repeated, and the VA post-MR should be recorded.

^d IOP measured via applanation tonometry should be measured at baseline using standard of practice at each site with the same method to be used for all consecutive visits in the study.

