10.2 LIST OF ANTICIPATED POTENTIAL ADVERSE EVENTS

Anticipated potential adverse events include those that might reasonably be expected to occur in this study because they are associated with dry eye disease, the risk analysis for TearCare System (albeit remote likelihood) or study testing methods.

- Eyelid/eye pain requiring discontinuation of the procedure
- Eyelid/eye pain ≥ 1 day after the procedure
- Burn, erythema, or swelling of the eyelids
- Thermal injury to the eye, including conjunctiva, cornea or lens
- Physical pressure-induced injury to the eyelid

- Corneal deformation
- Foreign body sensation
- Formation of a chalazion or stye
- Infection of the eyelid or ocular surface
- Ocular surface irritation or inflammation (e.g. Conjunctival injection, conjunctival or corneal abrasion, chemosis)
- Allergic or inflammatory reaction to the SmartLid or LipiFlow activator
- Loss in BCVA (ETDRS) of ≥ 10 letters

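### Acuity letters read at 1 m are counted like letters read at 4 m, so a severe loss is understated by about 30 letters and, for some eyes, can miss the 10-letter flag

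*Combined protocol and SAP*

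**What the plan says.** All references are to the combined protocol and SAP.

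- **Distance.** Section 21.2 says that acuity "will be measured using the ETDRS charts at 1 or 4 meters". Testing starts at 4 m, and "If the subject is unable to read line 1 (20/200) at 4 meters, then visual acuity testing should be performed at 1 meter". Later in 21.2, acuity testing for a subject is to be kept consistent from visit to visit, with viewing distance named among the conditions to hold constant.
- **Scoring.** "Each letter read correctly is recorded as one. Only move to the next line if 4 or more letters are read correctly". Then: "The number of correct letters will be recorded on the study worksheets and entered into the EDC". The only distance adjustment in 21.2 is optical: +0.75 sphere for refraction at 1 m.
- **Stopping.** Besides the four-letter rule just quoted, 21.2 says: "When it becomes evident that no further meaningful readings can be made despite encouragement to read or guess, the examiner should stop".
- **Correction.** Baseline and Month 1 acuity follow manifest refraction. On Day 1 and Week 2 (Section 9.1, Table 3, note c), acuity "is measured without manifest refraction (MR). If the VA has worsened by ≥ 10 letters (per ETDRS) from baseline, then MR should be performed", the test repeated and the refracted value recorded. The EDC instruction in 21.2 for two measurements names Day 1 only.
- **Use.** "Loss in BCVA (ETDRS) of ≥ 10 letters" is an anticipated adverse event in Section 10.2. Change in BCVA is a secondary safety endpoint, summarised by arm and visit (Sections 12.6.4 and 22.2.4). Inclusion criterion 8 requires 20/100 or better in both eyes.

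**The concern.** A change score has meaning only if both values are on one scale. At 1 m the same chart subtends four times the angle, so a letter read there is much easier than a letter read at 4 m. The text gives both one point and subtracts across distances. The error is one-sided: an eye that can no longer read the top line at 4 m is given an easier test, and the easier score is set against its baseline.

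Those are the eyes with severe loss. The treatment heats the eyelids, and Section 10.2 anticipates thermal injury to the cornea or lens. The 10-letter loss is both the trigger for repeat refraction on Day 1 and Week 2 and a listed adverse event, so a wrong count affects individual flags as well as the summary tables. The conflicting stopping sentences raise a smaller question of the same kind.

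**Working it through.** **The section's own figures.** The documents derive no sample size, power or test for BCVA, so there is no such figure to reproduce. The distances in 21.2 do check: 4 m = 157.48 in (stated 157.5), 1 m = 39.37 in (stated 39 3/8), and the lens add is 1/1 − 1/4 = 0.75 D (stated +0.75). The optics were adjusted for distance; the letter count was not.

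**Size of the distance offset.** log10(4/1) = 0.602. On an assumed standard chart (5 letters per line, 0.1 log steps, line 1 = 20/200 at 4 m) that is about 6 lines, or 6 × 5 = 30 letters.

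Let b be the baseline letters at 4 m and s the follow-up letters at 1 m.

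- Recorded loss = b − s
- Same-scale loss = b + 30 − s

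By criterion 8, b is at least 20 (20/100), so every eligible eye reads line 1 at 4 m at baseline. Counting whole lines, the best acuity that fails line 1 at 4 m is 20/250, which is s = 30.

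| Baseline (4 m letters) | Follow-up (1 m letters) | Recorded change | Same-scale change | 10-letter flag |
|---|---|---|---|---|
| 20/100 (20) | 20/250 (30) | +10 | −20 | missed |
| 20/80 (25) | 20/250 (30) | +5 | −25 | missed |
| 20/63 (30) | 20/250 (30) | 0 | −30 | missed |
| 20/50 (35) | 20/250 (30) | −5 | −35 | missed |
| 20/50 (35) | 20/320 (25) | −10 | −40 | raised |
| 20/40 (40) | 20/250 (30) | −10 | −40 | raised |
| 20/20 (55) | 20/250 (30) | −25 | −55 | raised |

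The flag is missed when b − s < 10. With s at most 30, that requires b < 40, a baseline just worse than 20/40. In every row the loss is understated by 30.

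**If the same-distance sentence is followed instead.** The eye falling from 20/100 to 20/250 stays at 4 m, scores about 0, and records a loss of 20, which is flagged. The two sentences therefore give +10 or −20 for the same eye. Staying at 4 m has a floor, however: a fall from 20/100 to 20/400 also scores about 0 and records 20, against a same-scale loss of 20 + 30 − 20 = 30.

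**Stopping sentences.** The documents give no letter-reading curve, so a range was simulated: a logistic curve with guess rate 0.1 and slopes of 0.2 to 1.0 lines, 40,000 tests per setting. Read-on means continuing until a line yields nothing. The true loss is 10 letters.

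| Slope | Read-on minus four-letter rule, mean letters | P(recorded loss < 10): four-letter rule at both visits | Four-letter then read-on: mean loss; P(< 10) | Read-on then four-letter: mean loss; P(< 10) |
|---|---|---|---|---|
| 0.2 | 0.5 | 0.36 | 9.45; 0.46 | 10.52; 0.31 |
| 0.4 | 1.2 | 0.41 | 8.75; 0.59 | 11.18; 0.28 |
| 0.7 | 2.7 | 0.44 | 7.22; 0.72 | 12.69; 0.20 |
| 1.0 | 4.5 | 0.45 | 5.33; 0.81 | 14.57; 0.14 |

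With one rule at both visits the mean recorded loss is 10.0 at every slope; the 0.36 to 0.45 is chance variation around a loss sitting on the threshold. Mixing rules shifts the mean by about 0.5 to 4.5 letters, in either direction.

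**Spectacles on Day 1 and Week 2.** Recorded loss = true loss + g, where g ≥ 0 is the number of letters forgone by not refracting. A true loss of 10 is recorded as at least 10. A true loss of 5 with g = 5 records 10, is refracted, and the excess is removed. A true loss of 5 with g = 4 records 9 and stays in the table. The direction is always towards more loss.

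**The case against.** Several points on the other side stand.

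- **The affected group is narrow.** Only eyes that start worse than 20/40 and can no longer read 20/200 at 4 m can escape the flag, and even then only when the same-scale loss is under 40 letters.
- **Other routes exist.** A reader might infer that a masked loss would go unnoticed altogether. The documents do not support that. Section 21.2 derives a Snellen equivalent, Table 3 schedules slit lamp and adverse event assessment at every follow-up visit, Section 10 requires all ocular events to be documented, and Section 10.1 treats sight-threatening events as serious and reportable.
- **The worksheet is unseen.** Letters are tallied on a Visual Acuity Worksheet that is not in the documents and may carry a conversion. The gap is established for the protocol text only.
- **Spectacle testing hides nothing.** A reader might infer that testing without refraction on Day 1 and Week 2 masks real losses. It does the reverse, and Section 9.1 sends apparent losses of 10 or more to a refracted repeat. What remains is that summaries at those visits mix refracted and unrefracted values.
- **The stopping conflict has no fixed direction.** It hides loss only if the four-letter rule is used at baseline and the looser one at follow-up. Section 9.8 asks for the same assessor throughout, although it allows an alternate, and 21.2 asks for consistency.

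None of this removes the distance defect. The same-distance sentence does not cure it, because it contradicts the 1 m switch without saying which governs.

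**Conclusion.** The point holds in a limited form. As written, Section 21.2 sets a 1 m letter count against a 4 m baseline and so understates loss by about 30 letters. For baselines from 20/100 to just worse than 20/40, a same-scale loss of 20 to 39 letters can be recorded as less than 10, or even as a gain. Better eyes are flagged, but the size of their loss is wrong. This rests on a standard chart, whole-line scoring and no conversion on the worksheet; reading part of a line would move the band's edges by a few letters.

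The eyes concerned should be rare. Change in BCVA is a descriptive secondary safety endpoint, so the primary analyses, alpha, power and sample size are untouched. The point is still worth acting on, because a stated scoring rule gives a wrong safety value for the severe losses the measure is there to detect. The stopping sentences and the Day 1-only EDC rule are smaller matters of consistency.

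**What to change.** In Section 21.2:

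1. Reconcile the switch to 1 m with the sentence asking for the same viewing distance at each visit.
2. State one letter scale for both distances: add 30 to every 4 m score, or subtract 30 from every 1 m score. If the worksheet already does this, say so in the text.
3. Add an EDC field for test distance. Where the distance is already in source records, existing scores can be rescaled.
4. Replace the two stopping sentences with one rule, used at every visit.
5. Extend the EDC rule for two measurements from Day 1 to Week 2, to match note c of Table 3.

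In the BCVA tables, label Day 1 and Week 2 values as unrefracted unless they were repeated after refraction.

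The cost is a few sentences in Appendix A, one EDC field and a table footnote. No new test, visit or staff is needed.
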